12.10f) The research could not practicably be conducted without the waiver or alteration

Agree Disagree

12.10f2) Describe how the waiver/alteration enables the research to be conducted

The HIPAA waiver enables study to be conducted because by reviewing patients CPRS records we will be able to determine if there are any exclusion criteria prior to the in-person screening to ensure there are no immediate exclusion criteria that would make the veteran ineligible (name and last 4 of SS# will be requested). If the participant is eligible based on their CPRS record findings and they are interested participating, they will be scheduled for an in-person screening. If participants are deemed to be ineligible after the in-person screening, then all information, including their responses will be shredded

12.10g) The research could not practicably be conducted without access to and use of the PHI

Agree Disagree

12.10g2) Describe why it would be impracticable to conduct this research without the PHI described 12.10a. (v3/8/18)

We request the use of PHI (name and last 4 of SS# will be requested) for screening purposes, appointment scheduling, and follow up (contact information), electronic payment as well as record review for inclusion exclusion criteria.

Section 13 - Alternatives to Participation

13) Describe the alternatives to participation in this research study (see ? for guidance)

Alternatives are to not participate in the study. All participants who do not wish to participate in the study or who are not eligible will complete the regular outpatient program at the VASDHS. Referrals to appropriate mental health services within VASDHS will be given if needed and/or requested.

Section 14 - Potential Risks

14) Describe any potential or known risks or discomforts and assess their likelihood and seriousness. (see ? for guidance)

Potential Risks: Potential risks associated with participation in the study are: 1) loss of confidentiality; 2) feeling uncomfortable during the assessment or therapy process either due to talking about trauma, emotional topics, or symptoms; 3) becoming more anxious, depressed, or developing suicidal thinking; 4) increasing one's alcohol or other illicit drug use; 5) therapeutic risks associated with Topiramate use; 6) discomfort, bruising, or other possible risks of venipuncture (inserting a needle into a vein to draw blood). Number 1 and 6 are research risks, number 2 is both a therapeutic and research risk; numbers 3, 4, and 5 are therapeutic risks; 7) The genetic testing portion of the study entails a small chance for loss of confidentiality which could affect employment or insurance. However, discrimination based on genetic information is now illegal.

Numbers 1), 6)and 7) are research risks, number 2) is both a therapeutic and research risk; numbers 3), 4) and 5) are therapeutic risks.

Section 15 - Risk Management

15) Describe the procedures for protecting against or minimizing any potential risks/discomforts, and the adequacy of resources for conducting the study and resources participants may need as a consequence of the research. See ? for further requirements.

The following steps will be taken to minimize the risk to confidentiality.

1) All data and saliva samples will be identified only with participant numbers, never with names or initials. All data will be stored in locked filing cabinets in offices at the VA or the PI's secure VA research folder in the VA research drive, and only study personnel will have access to the data. The list associating names and participant numbers will be stored in a locked cabinet separate from that in which other study data will be stored, and only the PI and project coordinator will have access to the key. Research staff will not release any information to anyone other than the

participant without that participant's consent. Participants will not be identified by name or other identifying features in any publication resulting from this research. Audio recordings will only be reviewed for supervision, reliability, and treatment adherence purposes and recordings will be erased as soon as data are analyzed.

2) To minimize the risk of patient discomfort, confidentiality will be stressed, participants will be offered breaks as needed, they will be informed that they have the right to refuse to answer questions or to terminate their participation in the study at any time without prejudice, and everyone who interacts with participants will be trained and supervised. Clinical staff will be available at each location if immediate in-person evaluation is required for medical or mental health issues.

3) and 4) To minimize the risk of patients becoming more anxious or depressed or increase drinking, every patient will be given a 24-hour contact phone number to call in the event of increased symptoms. During each assessment, the independent evaluator (IE) will assess for any major changes in health (e.g., overnight hospitalizations), possible adverse events, suicidal ideation, and general well-being. Study clinicians, during medication and psychotherapy visits, will assess for clinical worsening as part of the session protocols. If worsening symptoms are detected at any visit, a study clinician will be available to evaluate the patient and refer to appropriate treatment if needed. When in doubt, the decision whether continued participation in the study is safe and clinically warranted will always be on the side of patient safety. If a therapist or assessor identifies worsening substance use, the study investigators will evaluate whether best clinical care indicates a need for continuation in the study or more intensive SUD treatment. Participants will complete the Substance Use Inventory (SUI) at each session which will show worsening substance use. Therapists will be trained to contact the PI if a participant reports three or more days per week of alcohol use with more than four standard drinks or three or more days of illicit drug use in a week. If more intensive treatment is appropriate, we will assist the participant in obtaining the appropriate treatment. If the treatment is counter to study criteria, then we will discontinue the participant from the study following a final evaluation.

Adverse events, including those unlikely to be the result of participation in the research (e.g., hospitalization due to an automobile accident), will be monitored at every study contact, including medication, psychotherapy and assessment visits. They will be reported to the appropriate human subjects committees as per policy.

There is always a risk associated with the management of patients with AUD or PTSD that they will develop suicidality. This risk will be carefully mitigated by the systematic and careful assessment of suicidality throughout the protocol. This will be carefully done via the assessment measures to be completed by the participants, in-session assessments made by the therapists, and through comprehensive suicide risk assessments that are part of standard VA care. Participants who develop suicidality will be evaluated by a study clinician and investigators to determine whether continued participation in the study is safe and clinically warranted. If the study personnel and participant feel that treatment not allowed in the protocol is indicated (e.g., a different form of medication or psychotherapy, or hospitalization), an endpoint evaluation will be done, the participant will be discontinued from the study, and the participant will be referred for appropriate treatment.

5) Participants will be informed of the risks associated with the use of Topiramate, including all clinically significant warnings provided by the manufacturer in the medication package insert. This includes all current warnings and cautions in the most recent FDA guidelines dated May 2019 [95]. Given our frequent monitoring and standardized assessment of mood changes, we are already in compliance with the FDA's recommendation to monitor for this potentially rare adverse event. Participants will be informed that, as with any drug, Topiramate administration may involve other risks that are not known at the present time. If the study staff learns of any new possible risk or side effects of this drug, participants will be notified immediately. Participants will be informed that their condition may remain the same or deteriorate due to an ineffective treatment. They will also be informed of the availability of alternative treatments to facilitate alcohol use reduction. Participants will be told that if, in the opinion of the doctor, there are problems caused by their participation in the study that make it unwise for the participant to continue, their participation will be stopped. Patients who are discontinued from the study for any reason will be given a referral for further treatment if indicated.

All eligible participants will receive a laboratory diagnostic evaluation consisting of a chemistry panel, complete blood count, liver function tests (LFTs), urine toxicology screen and pregnancy test during their screening and/or randomization appointments so that participants with any illnesses that might adversely be affected by their participation in the trial will be excluded.

6) The risks of simple venipuncture commonly include the occurrence of discomfort and/or bruising at the site of the puncture. Less commonly, fainting, the formation of a small blood clots or swelling of the vein and surrounding tissue, or bleeding from the puncture site may occur.

There could be infection at the site where the blood was drawn. All blood draws will occur at the VA lab by certified professionals.

Additional safety measures are as follows: 1) we will recruit individuals with AUD/PTSD who are seeking treatment to reduce alcohol use and symptoms; 2) a careful intake assessment will be conducted and patients in need of immediate psychiatric treatment for severe depression or other conditions will not be enrolled and provided referrals; 3) our team consists of clinicians with extensive experience in the treatment of patients with AUD and PTSD; 4) study therapists will review all active cases weekly with the PI and therapy supervisor, and all members of the research team will immediately communicate any health or psychiatric-related problems to the PIs who will ensure that necessary safety steps are implemented; and 5) participants who are discontinued from the study will be scheduled for a final evaluation within one week and given appropriate treatment referrals. Participants discontinued due to a serious adverse event will be followed clinically by medical staff until the adverse event is resolved or becomes stable. Reasons for discontinuation and referrals made will be documented in the participants' casebooks.

Psychiatric Emergencies

If exacerbation of psychological symptoms occurs, members of the research team will discontinue assessment and assist the subject to access care.

Telephone assessments - All risk management and emergency response procedures would be followed in accordance with the protocol and we will use all procedures to mitigate risk when talking with a participant by phone during screening or scheduling appointments. In an effort to decrease risks associated with telephone screening, the veteran will be given the information to the nearest VA Health Center to their new residence and a licensed clinical psychologist will be available over the phone for crisis counseling if such an even should occur during any research procedure for the study.

Section 16 - Privacy and Confidentiality

16a) Provide a brief description of how participant privacy and confidentiality will be protected in this study.

Only approved study personnel will have access to study data, and all study personnel have been trained regarding privacy and security issues. In the event of a real or suspected breach of security, the VA Police, the VA Information Security Officer, and the VA Privacy Officer will be notified. Secure information will be accessed, stored, and destroyed according to a data security plan that will promote security and privacy, including, but not limited to the following:

Identifiers will be removed from study data following guidelines outlined by VA Handbook including 1605.1 Appendix B. We will assign Veterans a study identification number unrelated to identifying information. We will create a master list linking the study identification number to the Veteran record. The master list will be maintained by the Principal Investigator and stored in a locked cabinet in her laboratory. Access to the master list will be limited to the P.I. and her designees, all of whom will have completed VA IRB training requirements.

We will create and maintain a separate password-protected electronic study database containing the study identification number and study data specified above as well as genotype data from salivary samples. Individually identifiable health information (IIHI), as defined by Health Insurance Portability and Accountability Act of 1996 (HIPAA, Title II) will not be included in the study database. Specifically, we will exclude the 18 elements outlined by the Privacy Rule of HIPAA (section 164.514 and VA Handbook 1605.1 Appendix B) and "safe harbor" definition. Social security numbers will only be used to look-up medical records, and will not be maintained as data. Further, we will make all necessary efforts to insure a Veteran may not be identified via extraction of any combination of the data maintained in the study database in which identifiers have been removed. Access to the study database will also be limited to the P.I. and her IRB trained designees.

Electronic VASI

Audio Recordings: All treatment sessions and interviews will be recorded on digital audio recorders "Sony ICD-UX533", "Sony ICD-PX333", "Olympus VN-1800", "Olympus VN-6200PC", "Olympus Vn-7200", "Olympus DP-201 and the "Olympus VN-6300pc" will be used in this study and placed on VA service for potential review by supervisors. These recorders will be stored in a locked cabinet in bldg. 1, room 2341. The audio recordings will be downloaded to the VA R:\drive. Copies of randomly selected interviews will be reviewed by [name], who is a VASDHS employee and can review the information without removing it from VA grounds. Recordings will

be destroyed in accordance with the most current VA Records Control Schedule guidelines and in consultation with the VASDHS ISO and VASDHS IT Department Personnel.

In the event of a suspected security breach, we will notify the VA Privacy Officer, VA Police, and VA Information Security Officer.

Refer to the VA Privacy and Data Security Plan for further detail.

16a2) See Privacy and Data Security Plan for further details.

Yes No

16b) Is SSN used for any purpose other than scanning Consent/HIPAA into the medical record? (e.g., subject payments, use of clinical record)

Yes No

16b2) If YES, indicate purpose and justification:

Social security numbers will only be used for use of clinical records, or subject payments and will not be maintained as data. Further, we will make all necessary efforts to insure a Veteran may not be identified via extraction of any combination of the data maintained in the study database in which identifiers have been removed.

Section 16.1 Entry of CPRS Notes

16.1) Entry of a CPRS Research Informed Consent Note is required if any of the following apply:

- The subject is admitted as an inpatient or treated as an outpatient for research
- The study involves research medical care or may affect medical care.
- The Informed Consent and HIPAA Authorization indicate notes will be entered

Notes: Scanning the Consent and HIPAA Authorization into CPRS is no longer required. Linking the Consent to the Research Informed Consent Note is permitted (Unless the study has a Certificate of Confidentiality) and may be especially useful for trials involving the Research Pharmacy. For Non-Veterans, if Research Informed Consent Notes are entered then the NOPP Acknowledgement must be scanned in. A Research Progress Note should also be entered for each procedure or intervention. Address the CPRS note requirement:

16.1a) Is entry of CPRS notes required based on the above criteria?

Yes No

16.1b) Are CPRS notes entered?

Yes No

16.1c) Is a CPRS waiver is requested instead?

Yes No

Section 17 - Potential Benefits

17) Discuss benefits that may be gained by the subject as well as potential benefits to society in general. (see ? for guidance)

The potential benefits for participants include decreased distress and alcohol use and improved quality of life. Study of the effectiveness of Topiramate and PE will also benefit individuals who have AUD and PTSD and society more generally by providing information about how best to treat co-occurring AUD and PTSD.

Section 18 - Risk/Benefit Ratio

18) Discuss why the risks to subjects are reasonable in relation to the anticipated benefits to subjects and in relation to the importance of the knowledge that may reasonably be expected to result.

The potential benefits of improved understanding of how to manage patients with PTSD and AD outweighs the potential risks of this study.

Section 20 - Compensation for Participation

20) Provide all details and justifications of the compensation plan. See [?](#) for detailed requirements.

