TOP Titration Schedule, Dosage Considerations, and Duration of Treatment. To increase medication tolerability, dosages of TOP will be gradually titrated upward (weeks 1-5) on a fixed schedule as shown in Table 1 . Participants will continue on this dosage of medication for 10 weeks (weeks 6-16) until a more rapid dosage titration (i.e., 50 mg twice daily for 4 days, then 25 mg twice daily for 3 days) downward occurs. This latter dosage titration is intended to minimize any discontinuation syndrome that may occur in patients treated with TOP.

Several prior studies of TOP have used a maximum target dose of 300 mg [5]. However, a recent meta-analysis of TOP found 200 mg to be effective for treating AUD [5] and VA/DoD guidelines recommend 200 mg per day for the treatment of AUD due to lower side effects than at 300 mg [2]. We made the decision to use TOP at a maximum target dosage of up to 250 mg to take into account the recent findings and recommendations as well as the literature that used 300 mg as the maximum dosage. Therefore, we will use a maximal target dosage of 250 mg. in these AUD/PTSD participants and will carefully monitor adverse effects .

Every attempt will be made to maintain participants at the maximal TOP dosage specified above. Studies by us and other investigators using maximal dosages of TOP of approximately 200 mg per day have found that approximately 90% of participants were able to take the full maximal dosage. However, participants who are unable to tolerate the specified dose will be allowed to continue in the study at a reduced dose (the maximum tolerated dose) as determined by the research physician. Such participants may continue to participate in all other aspects of the study. When TOP/placebo dosage reduction is warranted due to adverse side effects, the research physician will decrease the medication dosage by one step at a time as shown in the dosage titration schedule from the maximum to the amount that is clinically tolerable. As dosage reductions are permissible in all groups, this will not break the blind. In the case of severe side effects, discontinuation of the study agent may be necessary. In such a situation, a research physician will evaluate the patient to determine whether the study agent should be discontinued immediately or should be tapered to discontinuation.

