Medication Blinding Plan. Study participants and treatment providers will be aware that participants will receive either active or inactive medications and that all are kept blind to medication received until the conclusion of the study. [name], the non-blinded VA San Diego Research Pharmacist, will assign participants to treatment group based on our randomization procedures and will manage the double blind. TOP and placebo tablets will be obscured by mixing with lactose, and over-encapsulated in identical opaque locking capsules to ensure blinding. The Research Pharmacist and a non-blinded, non-treating physician Safety Monitor ([name].) will have access to the medication randomization record in the event that the blind must be broken on an emergent basis.

Medication Dispensing. Study medication will be stored in the VA San Diego Research Pharmacy. Storage, packaging, dispensing and record keeping will be the responsibility of the Research Pharmacist, [name], in coordination with the study staff (i.e, the study coordinator and therapists) and Study Physicians. During the two dosage titration periods, capsules will be packaged in vials in accordance with the graduated dosing schedule described in the Titration section above. During the 10-week maintenance phase, capsules will also be packaged in vials by the pharmacist to be dispensed to participants at each scheduled visit. In the event that a participant misses a morning dose in the twice-daily dosage schedule, they will be instructed to take it later in the day. In the event that the patient entirely misses a daily dose, they will be told not to double-up on the capsules the following day. Since medication adherence is the focus of one of the concomitant psychosocial interventions, missed doses, problems with adherence, and strategies to improve compliance will be discussed regularly with each study participant. Participants will be asked to return unused medication at each visit to the Research Associate for capsule counts. Unused medication will be destroyed as per VA San Diego Research Pharmacy protocol.

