Participants will continue on this dosage of medication for 10 weeks (weeks 6-16), until a more rapid dosage titration (i.e., 50 mg twice daily for 4 days, then 25 mg twice daily for 3 days) downward occurs. This latter dosage titration is intended to minimize any discontinuation syndrome that may occur in patients treated with TOP.

Several prior studies of TOP have used a maximum target dose of 300 mg [5]. However, a recent meta-analysis of TOP found 200 mg to be effective for treating AUD [5] and VA/DoD guidelines recommend 200 mg per day for the treatment of AUD due to lower side effects than at 300 mg [2]. We made the decision to use TOP at a maximum target dosage of up to 250 mg to take into account the recent findings and recommendations as well as the literature that used 300 mg as the maximum dosage. Therefore, we will use a maximal target dosage of 250 mg in these AUD/PTSD participants and will carefully monitor adverse effects. Every attempt will be made to maintain participants at the maximal TOP dosage specified above. Studies by us and other investigators using maximal dosages of TOP of approximately 200 mg per day have found that approximately 90% of participants were able to take the full maximal dosage. However, participants who are unable to tolerate the specified dose will be allowed to continue in the study at a reduced dose (the maximum tolerated dose) as determined by the research physician. Such participants may continue to participate in all other aspects of the study. When TOP/placebo dosage reduction is warranted due to adverse side effects, the research physician will decrease the medication dosage by one step at a time as shown in the dosage titration schedule from the maximum to the amount that is clinically tolerable. As dosage reductions are permissible in all groups, this will not break the blind. In the case of severe side effects, discontinuation of the study agent may be necessary. In such a situation, a research physician will evaluate the patient to determine whether the study agent should be discontinued immediately or should be tapered to discontinuation.

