- 11) Individuals with clinically significant renal disease and/or impaired renal function, as defined by clinically significant elevation of blood urea nitrogen (BUN) or creatinine or an estimated creatinine clearance of < 60 mL/min, can be included with physician approval, however the dosing schedule and maximum dose will be adjusted in accordance with FDA prescribing guidelines,
- 12) if individual is on another addiction medication, they should be on a stable approved addiction medication dose (at least two weeks before starting study drug) throughout the study,
- 13) are capable of giving informed consent.

Exclusion criteria are:

- 1) Subjects known to have clinically significant unstable medical or psychiatric conditions, where participation is deemed by investigators and study physicians to be risky, including but not limited to:

-AST and/or ALT >5 times the upper limit of the normal range and/or an increased serum bilirubin >2 times the upper limit of normal.

-Seizure disorders

- 2) have been treated with Topiramate for any reason in the past and discontinued the drug due

to hypersensitivity reaction

3) in the opinion of the investigator, should not be enrolled because of the precautions, warnings, or contraindications listed on the Topiramate package insert, (e.g., certain types of glaucoma),

4) are pregnant, lactating, or plan to become pregnant during the period of participation in the study

5) in the judgment of the investigator, represent a significant risk of suicidal or homicidal behavior

Women and Minorities

Women comprise 11% (e.g., SAMI clinic) to 60% (Military Sexual Trauma clinic) of the Veterans seen in the clinics from which we will be recruiting, and approximately 24% of Veterans in the program are minorities. Consistent with SAMI demographics as a whole, 10% of participants in our current Merit study over the past 3 years have been women. We have been able to obtain 26% Hispanic, 16% African American, and 20% other ethnic groups, for a total of 52% from minority groups. We will continue attempts to oversample these groups to obtain adequate recruitment of females and minorities to examine effect sizes for these groups relative to male and Caucasian counterparts.

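### The single end-of-treatment taper is not reconciled with the reduced-dose and renal provisions: read literally, its first step (100 mg/day) is an increase for anyone taking less

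*Combined protocol and SAP*

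**What the plan says.** Section 9, under the topiramate titration heading, describes upward titration on a fixed schedule (Table 1) and then a maintenance period: "Participants will continue on this dosage of medication for 10 weeks (weeks 6-16"). The target is stated plainly: "Therefore, we will use a maximal target dosage of 250 mg". Maintenance ends when "a more rapid dosage titration (i.e., 50 mg twice daily for 4 days, then 25 mg twice daily for 3 days) downward occurs". Section 9.3 repeats the same taper with the same figures. In both places the purpose given is to limit discontinuation effects.

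The same two sections provide for participants who cannot tolerate the target. They "will be allowed to continue in the study at a reduced dose (the maximum tolerated dose) as determined by the research physician" and remain in the rest of the study. The physician lowers the dose step by step along the titration schedule until the participant can tolerate it. The text gives no lower limit for such reductions. Where side effects are severe, a physician decides case by case between an immediate stop and a taper to discontinuation; no taper doses are given for that situation.

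Section 10, inclusion criterion 11, concerns impaired renal function. Such participants "can be included with physician approval, however the dosing schedule and maximum dose will be adjusted in accordance with FDA prescribing guidelines". It does not mention the taper.

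Section 9, Medication Dispensing, covers the two titration periods, upward and downward: "capsules will be packaged in vials in accordance with the graduated dosing schedule described in the Titration section above". No variant is given for a participant on a reduced dose.

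**The concern.** The taper is written as two fixed daily amounts, not in relation to what the participant is taking, and it follows directly from a paragraph about the scheduled dose. A few sentences later the plan creates a group who are not on the scheduled dose, and it never returns to the taper for them. The packaging sentence then turns the written schedule into a dispensing instruction, and the only downward schedule it can refer to is the fixed one.

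The people in the gap are those for whom it matters most: participants already identified as unable to tolerate more drug and, if their adjusted dose is low enough, participants with impaired renal function. If the text were followed to the letter, a step intended to ease them off the drug would take some of them above the dose recorded as the most they could tolerate. The statistical analysis does not depend on this. It is a question of internal consistency and participant safety.

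**Working it through.** No sample size, power or alpha figure bears on this point, and the plan gives no figure to reproduce. The check is dose arithmetic plus a reading of the provisions side by side.

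**Inputs from the documents**

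- First taper step: 50 mg twice daily for 4 days (Sections 9 and 9.3).
- Second taper step: 25 mg twice daily for 3 days (same places).
- Maximal target: 250 mg/day (same places).

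**Input assumed**

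- The daily dose just before the taper, shown over a range. The actual steps are in Table 1, which is not in the text available for review. Its absence from that text is not counted as a fault in the plan.

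**Daily amounts**

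- First step: 2 × 50 = 100 mg/day.
- Second step: 2 × 25 = 50 mg/day.

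**Change = taper step minus pre-taper dose**

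| Assumed pre-taper dose (mg/day) | First step, 100 mg/day | Second step, 50 mg/day |
|---|---|---|
| 250 | −150 | −200 |
| 200 | −100 | −150 |
| 150 | −50 | −100 |
| 125 | −25 | −75 |
| 100 | 0 | −50 |
| 75 | +25 | −25 |
| 50 | +50 | 0 |
| 25 | +75 | +25 |

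The written taper does what it says for anyone above 100 mg/day. At exactly 100 mg/day there is no reduction for the first 4 days. Below 100 mg/day the first step is an increase, and below 50 mg/day the second step is also above the starting dose.

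**Could a dose below 100 mg/day arise?** Reductions go down the upward schedule one step at a time, so the answer lies in Table 1. As an illustration only, suppose 250 mg/day were reached in equal steps. Section 9 gives upward titration as weeks 1-5 in one place and as 6 weeks in the Design paragraph. Five steps would be 250/5 = 50 mg each, and six would be 250/6 = 41.7 mg each. Either way at least one step lies below 100 mg/day. This shows that such doses are plausible on the schedule. It does not show that anyone would be held at one.

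**How many?** The documents do not say. The titration text cites prior experience that about 90% of participants could take the full dose, but at about 200 mg/day rather than 250. It does not say how far the remainder were reduced.

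**Provisions set against each other.** The taper text describes a fall from the scheduled dose. The reduced-dose text puts some participants on another dose. Criterion 11 may put others on another schedule. The packaging sentence refers to one described schedule. Nothing in the text connects the four.

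**The case against.** The strongest reply is that the plan never says the fixed taper applies to everyone or that anyone's dose is to be raised. A reader might infer both, but the documents do not support either as a statement of intent. The taper is described from the scheduled dose and is called downward, and silence about participants on lower doses is not an instruction to increase. This stands, and it limits the point to a literal reading of text that was left unreconciled.

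Two provisions also leave room for judgement. Criterion 11 says the dosing schedule will be adjusted in renal impairment, and a taper can fairly be seen as part of a dosing schedule. Stopping for severe side effects is decided individually and carries no fixed doses, so it would be wrong to attach the 50 mg and 25 mg steps to participants who stop early. Both stand. Early stoppers are not part of this point, and the renal provision is cited only because it does not say whether the taper is adjusted too.

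The packaging sentence can likewise be read as describing the standard case. The text just before it has the pharmacist work in coordination with study staff and physicians. Read rigidly, it would also prevent dose reductions during upward titration, which the plan clearly allows. That is fair as to intent. It does not supply a rule: nothing written tells the pharmacist what to pack for the taper of a participant on a reduced dose.

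Finally, Table 1 might set a floor or address the matter. That cannot be excluded. What the reply leaves standing is that the plan's text states one absolute taper, allows lower doses, and does not say how the two fit together.

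**Conclusion.** Wrong as written: an internal inconsistency in the dosing text, probably affecting few participants. The arithmetic is certain. A first step of 100 mg/day is no reduction for someone taking 100 mg/day and an increase for anyone taking less, which conflicts with a step described as downward and with a dose defined as the maximum tolerated.

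The size in participants is unknown and could be zero. It depends on Table 1, on how far doses are in fact reduced, and on what is done in renal impairment. A reader might combine the roughly 90% figure with 60 per arm to get 10% × 60 = 6 active participants on reduced doses, and then guess a share below 100 mg/day. The documents do not support a count: the 90% was observed at about 200 mg/day and says nothing about the depth of reduction. A reader might also infer an excess of adverse events in the active arm. That would require the increase both to happen and to cause harm, and the documents show neither. No effect on the primary analysis is claimed.

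**What to change.** The sponsor and study physicians should:

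- reconcile the taper text in Sections 9 and 9.3 with the reduced-dose provision in the same sections and with inclusion criterion 11 in Section 10;
- state explicitly how the end-of-treatment taper applies to participants whose dose is at or below 100 mg/day, including those on a renally adjusted schedule;
- align the packaging sentence under Medication Dispensing with that decision.

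If Table 1 already settles the matter, a cross-reference from the taper text and the packaging sentence would be enough. The clinical decision belongs to the study physicians, and no dose or taper rule is proposed here.

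The cost is a short change to the protocol wording and a matching pharmacy instruction, with no additional visits or data. It should be settled before taper vials are packed for any participant on a reduced dose.
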